### 1.3.1 Subgroup of interest

For the analysis of the primary anaylsis the following fixed factors were included in model:

- HCV-(IgG), measured at screening in viral serology: positive vs. negative
- Lab MELD, measured at screening: <=30 vs >30

Descriptive statisitics for

Descriptive statistics for the primary efficacy variable were presented for the following subgroups:

- age: <60 vs.  $\geq$ 60 years
- gender: male vs. female
- renal function at baseline: 30 – <45, 45 – <60,  $\geq$ 60 mL/min/1.73m^2;
- renal function at baseline: <45 vs  $\geq$ 45 mL/min/1.73m^2,
- renal function at baseline <60 vs.  $\geq$ 60 mL/min/1.73m^2
- HCV status at baseline: positive vs. negative
- lab MELD score at baseline:  $\leq$ 14, 15 – 19, 20 – 24, 25 – 29,  $\geq$ 30

## 2 Statistical methods

### 2.1 Data analysis general information

The data were analyzed by [REDACTED]. Any data analysis carried out independently by the investigator(s) was submitted to Novartis before publication or presentation. The final analysis was done when all patients have completed their Visit 9 (Month 12) assessment or discontinued prematurely. The data from all centers that participate in this protocol was used, so that an adequate number of patients will be available for analysis.

Data were summarized with respect to demographic and baseline characteristics, efficacy observations and measurements, safety observations and measurements, and pharmacokinetic measurements. All summary statistics were presented by treatment group. Categorical variables were summarized by absolute and relative frequencies. Continuous variables were summarized by descriptive statistics of the number of valid observations, mean, standard deviation, minimum, median and maximum. Time-to-event data including rates of affected

patients were assessed by Kaplan-Meier statistics. Group comparisons were performed using appropriate two-sided statistical tests.

Analysis was carried out using the SAS (Statistial Analysis System) software, version 9.2, 2009, SAS Institute Inc., Cary, North Carolina, USA.

### **2.1.1 General definitions**

Study treatment:

- EVR/TAC
- TAC

Date of randomization: Date of Visit 2 (Baseline)

Date of first treatment: max (date of randomization, min (start date of dosage administration\*))

Date of last treatment: Max (max(end date of dosage administration\*), Last known date subject took study treatment~)

\*: documented on Dosage Administration Record form

~: documented on End of Treatment form

## **2.2 Patient disposition, demographics and other baseline characteristics**

Demographic and other baseline characteristics were summarized for the full analysis set (FAS) by treatment group. Baseline characteristics include prior medication, past/current medical conditions and transplant history.

Medical history was coded using MedDRA and was presented by MedDRA system organ class, preferred term and treatment group. Separate tables were provided for past medical conditions and current medical conditions. Prior medication was coded according to the WHO Drug Reference List and summarized by ATC class, preferred term and treatment group.

### **2.2.1 Patient disposition**

Patient disposition was summarized for all patients by absolut and relative frequencies of patients completing the study phases screening, randomization,treatment and study completion. Reasons for discontinuation of screening, treatment and study were shown by treatment for all patients (screening) resp and the randomized set (treatment and study).

The number of patients per analysis set was summarized by treatment.

Protocol violations were reported descriptively by treatment.

## **2.3 Treatments (study treatment, rescue medication, concomitant therapies, compliance)**

### **2.3.1 Study treatment / compliance**

Duration (days) of drug exposure to each individual component of the immunosuppressive treatment regimen was summarized using descriptive statistics. Duration of drug exposure was calculated as the difference between the last and first day of drug application +1. Dosage averages were calculated including and excluding zero doses for periods of temporary interruption of treatment regardless of whether this was due to safety reasons or patients' non-compliance. Daily dose levels were summarized descriptively. Frequencies of the number of patients with any dose reduction (including temporary dose interruption) as well as the number of dose reductions by reason were given. These analyses were performed by treatment group for the safety set.

Frequency tables displaying cumulative frequencies of 'crude rates' will be presented for the number of patients with trough levels below/within/above the defined therapeutic windows drug and by visit.

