## 4 Study design

This is a 12-month, multi-center, open-label, randomized, controlled study to evaluate efficacy and safety and evolution of renal function of everolimus (EVR) in co-exposure with tacrolimus (TAC) in *de novo* liver transplant recipients.

Patients will be consented and screened for eligibility prior to liver transplantation (LTx). The study treatment will start with a run-in period that ends on the day of randomization (RND), scheduled at 7-21 post- LTx. Patients after consent who have undergone successful LTx (with optional induction therapy) will be entered in this run in period (between 3 and 5 days post- LTx) and may be initiated on an optional induction therapy, MMF, TAC at investigators' discretion until at least day 7 or maximally until day 21 post LTx with mandatory CS therapy until at least Month 6 post Tx.

Patients on MMF according to local practice must have the MMF administration discontinued by the time of RND. MMF is discontinued according to local practice.

At day 7-21 post-transplantation the following information at minimum has to be obtained from a patient to be randomized into the study:

- Abbreviated MDRD eGFR > 30 mL/min/1.73m^2. Creatinine results obtained in local laboratory within 5 days prior to RND are acceptable.

All eligible patients (according to in-/exclusion criteria at RND) will be randomized in between 7 and 21 days post LTx to one of the two treatment groups in a 1:1 ratio:

**Arm 1: EVR/TAC group** (Tacrolimus minimization arm)

Everolimus should be initiated at the day of randomization. Therapeutic drug monitoring will be mandatory throughout the duration of the study. Whole blood trough levels should be obtained  $5 \pm 2$  days after either everolimus or tacrolimus doses are changed.

**Everolimus dosing:** Everolimus study drug will be started at the day of randomization at a dose of 1.0 mg b.i.d (2.0 mg daily dose). The everolimus whole blood trough (C-0h) levels should be targeted to be maintained between 3-8 ng/mL. The twice daily dose can be changed in order to maintain the 3-8 ng/mL C-0h levels through the remainder of the study.

**Tacrolimus dosing:** After everolimus whole blood trough levels have been confirmed to be in the target range (3-8 ng/mL), tacrolimus tapering should begin, achieving a target tacrolimus C-0h levels of <5 ng/mL plus corticosteroids by three weeks after randomization and continuing through the remainder of the study.

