## **7.7 Tolerability/acceptability**

Tolerability of study medication can be assessed from the rate of patients who withdraw prematurely from study medication or in whom study medication had to be converted to another immunosuppressive regimen due to abnormal laboratory results, adverse events, or toxicity.

All changes to the immunosuppressive medication dosing regimen will be recorded on the Dosage Administration Record CRF, along with the reason for change.

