- To evaluate the incidence of and time to renal replacement therapy as concomitant therapy of special interest.

Safety related secondary objectives were

- To evaluate the incidence of Adverse Events (AEs)/Infections/Serious Adverse Events (SAEs).
- To evaluate the incidence of treatment-related side effects, including incidence of new onset diabetes mellitus (NODM), evolution of metabolic parameters as subdivisions of serum/plasma lipid panel, neurotoxicity and hypertension.
- To evaluate the incidence and reason (e.g. AE) of premature discontinuation of study medication and premature discontinuation from the study.
- To evaluate the incidence and reason (e.g. AE) of interruption and dose adjustment of study medication.

Virus (HCV, CMV) and Hepatocellular Carcinoma (HCC) related secondary objectives were

- To evaluate the incidence of HCV and HCV related fibrosis.
- To evaluate HCV viral load (HCV- messenger ribonucleic acid (mRNA) levels overall and by genotype).
- To evaluate incidence of and response to HCV antiviral treatment.

- To evaluate the rate of recurrence of HCC at 12 post-transplantation in patients with a diagnosis of HCC at the time of liver transplantation adjusting for various risk factors, such as number of tumor nodules, total tumor size and tumor metastasis.
- To evaluate the incidence of de novo HCC malignancies. (adverse event of special interest)
- • Incidence and severity of CMV viral infections.

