## 5 Appendix

### 5.1 Imputation rules

#### 5.1.1 Study drug

According to Novartis-Germany guidelines missing values in dates will be imputed by a simple way:

Missind day → replacement by 15

Missing month → replacement by 7

Everolimus and Tacrolimus are study medication. After treatment discontinuation this treatment are documented as "Immunosuppressive Medications". For the analysis of Everolimus and Tacrolimus this treatment have to be shifted from "Immunosuppressive Medications" to Study medication. If WHO-DD-preferred-name are EVEROLIMUS or TACROLIMUS, TACROLIMUS MONOHYDRATE in "Immunosuppressive Medications", the record will be shifted to "Study medication". If the end-date of the medication is later than the last visit (e.g. Month 12) or the medication is "continuing after study", the end-date will be set to date of last visit. This adaption is necessary to calculate the treatment duration and the mean dose over the study for everolimus and tacrolimus.

Duration of exposure will be calculated until end of study. That means, that the period after end of treatment will also be included.

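### The by-arm count of patients with any dose reduction does not separate Arm I's required tacrolimus taper, or trough-guided changes, from reductions for toxicity

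*SAP*

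**What the plan says.** One of the safety objectives is "To evaluate the incidence and reason (e.g. AE) of interruption and dose adjustment of study medication" (SAP 1.3; the same objective is in protocol 3.2).

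The output that serves it is in SAP 2.3.1, which follows protocol 10.3.1: "Frequencies of the number of patients with any dose reduction (including temporary dose interruption", and in the same sentence "as well as the number of dose reductions by reason were given". On layout and population the SAP adds: "These analyses were performed by treatment group for the safety set". Neither document defines a dose reduction, says which drug it refers to, or excludes changes that the protocol itself requires.

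SAP 5.1.1 states: "Everolimus and Tacrolimus are study medication". For Arm I, protocol Section 4 requires a change in one of those two drugs after randomization: "tacrolimus tapering should begin, achieving a target tacrolimus C-0h levels of <5 ng/mL plus corticosteroids by three weeks after randomization". The taper has a precondition: "After everolimus whole blood trough levels have been confirmed to be in the target range (3-8 ng/mL". Arm II has no taper; its tacrolimus trough is to be held at 6-10 ng/mL. In both arms protocol 6.6.3 also calls for tacrolimus dose changes whenever the trough is out of range, and in Arm I the same applies to everolimus.

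The reason for each change is to be collected. Protocol 7.7 says: "All changes to the immunosuppressive medication dosing regimen will be recorded on the Dosage Administration Record CRF, along with the reason for change".

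**The concern.** A patient in Arm I who follows the protocol exactly and has no toxicity can still enter the count, because lowering tacrolimus is part of the assigned regimen. A comparable Arm II patient enters only for a trough above range or for intolerance. The two patient counts therefore measure different things.

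The objective asks for incidence, which is a count of patients, together with the reason. The planned output gives patients without reason and reductions with reason, and the second cannot be turned into patients by reason because one patient may contribute several reductions. A reader who compares the two arms on the patient row could take a feature of the design for poorer tolerance of the everolimus regimen. A real difference in AE-driven reductions, in either direction, could be hidden.

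**Working it through.** The plan states no dose-reduction rate, so there is no figure to reproduce. The check has two parts.

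**Part 1: does the taper fall inside the count as written?**

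- *Drug.* Tacrolimus is study medication under SAP 5.1.1, and SAP 2.1.1 defines study treatment by regimen (EVR/TAC or TAC). Read plainly, any dose reduction covers tacrolimus.
- *Time window.* Under SAP 2.1.1 treatment cannot start before randomization. The Arm I taper follows randomization, so it lies inside the window.
- *Arm.* Protocol Section 4 requires the taper in Arm I only.
- *Reason.* The by-reason split applies to reductions, and neither document names a reason category for the planned taper or for trough-guided changes.
- *Other outputs.* The SAP also reports reasons for treatment discontinuation (2.2.1) and AEs leading to permanent discontinuation (2.6.1). Neither covers dose reductions, so SAP 2.3.1 is the only planned output for the dose-adjustment objective.

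Nothing in the text keeps the taper out of the Arm I patient count.

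**Part 2: how large could the effect be?**

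Two inputs are needed, and the documents give neither. Both are assumptions:

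- f = share of Arm I patients with a recorded taper step. Run-in tacrolimus is at the investigator's discretion (protocol Section 4), so the share who start above 5 ng/mL is unknown.
- r = share of patients with any other reduction or interruption, taken as equal in the two arms and independent of the taper.

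Then Arm II = r, Arm I = 1 - (1 - f)(1 - r), and the difference due to the taper alone = f(1 - r).

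| f | r | Arm I | Arm II | Difference (points) |
|---|---|---|---|---|
| 0.50 | 0.2 | 60% | 20% | 40 |
| 0.50 | 0.8 | 90% | 80% | 10 |
| 0.80 | 0.2 | 84% | 20% | 64 |
| 0.80 | 0.4 | 88% | 40% | 48 |
| 0.80 | 0.8 | 96% | 80% | 16 |
| 0.95 | 0.2 | 96% | 20% | 76 |
| 0.95 | 0.8 | 99% | 80% | 19 |

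The extremes are 0.50 x (1 - 0.8) = 0.10 and 0.95 x (1 - 0.2) = 0.76. The difference is positive for every f above 0 with r below 1, so the direction does not depend on the assumptions; the size does.

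One asymmetry lies outside this calculation. Arm I has two trough-adjusted drugs and Arm II has one, so r itself may be higher in Arm I without any difference in toxicity.

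**The case against.** **Inclusion of the taper is inferred.** No sentence says that the row pools drugs or counts the taper. SAP 2.3.1 opens by summarizing exposure for each component of the regimen, so per-drug rows are a natural reading. Parts of the protocol treat everolimus as the study drug and name tacrolimus separately, and SAP 5.1.1 explains its reassignment of records by the needs of treatment duration and mean dose. This stands, and the point is conditional on tacrolimus being counted. But the per-component wording is attached to duration only. Per-drug rows would clear the everolimus row, yet the tacrolimus row, the only drug common to both arms, would still set a taper against maintenance.

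**Reasons are already reported.** A reader might infer that the dose-adjustment objective cannot be assessed at all. The documents do not support that: reductions are counted by reason, which gives partial information. What is missing is the number of patients by reason.

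**Tolerability is measured elsewhere.** Protocol 7.7 and 10.5.3 assess it by premature withdrawal from study drug or conversion to another regimen, and no test is attached to the dose-reduction row. This stands, and it confines the point to the dose-adjustment objective.

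**Stronger figures are tempting but unsupported.** A reader might infer that Arm I must be close to 100%. The taper waits on the everolimus trough, patients already below 5 ng/mL may need no reduction, and those who stop early may never taper. A reader might also assume a trough at randomization with mean 7.5 and SD 2.5 ng/mL. That puts 84% of Arm I at or above 5 ng/mL and 16% of Arm II above 10 ng/mL, an apparent gap of 84 - 16 = 68 points. It compares a single baseline trough in Arm II with a 12-month count in Arm I. Tacrolimus is measured at eight scheduled visits (Visits 2 to 9). If those troughs were independent, 1 - 0.84^8, about 75%, of Arm II would exceed 10 ng/mL at least once. With the same background in Arm I, the taper would add 0.84 x 0.25, about 21 points. Real troughs are correlated, so the answer would lie between, and no single figure can be defended.

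**Conclusion.** The point holds in a limited form. SAP 2.3.1 gives a patient count that, if tacrolimus is included, is raised in Arm I by design and cannot be compared between arms as a measure of toxicity-driven dose adjustment. The by-reason output does not repair this, because it counts reductions and not patients.

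The size cannot be derived from the documents. A taper-only difference of about 10 to 76 points is a range under assumed inputs (f from 0.50 to 0.95, r from 0.2 to 0.8, r equal in both arms and independent of the taper), not an estimate for this trial.

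The row is descriptive. The primary eGFR analysis, the key secondary composite, the sample size and the protocol's withdrawal-or-conversion measure of tolerability are unaffected. This is an inexpensive improvement to one safety table.

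**What to change.** In SAP 2.3.1, define a dose reduction for each drug and tabulate patients as well as events with a reduction or interruption, separately for everolimus and tacrolimus and by recorded reason. Use the number of patients with a reduction or interruption for an AE or laboratory abnormality as the between-arm row for the dose-adjustment objective. Show the protocol-required taper and trough-guided changes in rows of their own.

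The cost is a few lines of SAP text and one extra descriptive table, with no new data and no change to any treatment rule. The change depends on the recorded reasons separating AE or laboratory causes from planned or trough-guided changes. The documents say that a reason is collected but do not show its categories, so this should be checked on the Dosage Administration Record form first. If the categories do not separate them, the SAP should say so and state that the patient row is not a comparison of toxicity-driven dose adjustment.

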### **2.3.2 Prior, concomitant and post therapies**

Prior and concomitant medications and non-drug therapies were coded according to WHO-DRL. Concomitant medications taken through the study were summarized by preferred term, ATC class and treatment group for the safety set. Prior medication are defined as medication, which started 1 or more days before randomization. Concomitant medication are medication, which were treated on at least one in the time interval randomization and last day of study treatment

Corticosteroids will be displayed using prednisone equivalent body weighted adjusted doses. Analysis of the primary objective

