### **Renal function-related objectives**

[figure not shown]
- To evaluate the evolution of post-randomization renal function over time assessed by the change in estimated GFR (MDRD-4), including to Months 6, and 12.
- To evaluate renal function by eGFR using various methods (MDRD-4, Nankivell, Cockcroft-Gault, CKD-EPI and Hoek formulae).
- To evaluate the incidence of patients experiencing a decline in eGFR (MDRD-4) of  $< 10$ ,  $10-15$ ,  $15-20$ ,  $20-25$ , and  $\geq 25$  mL/min/1.73m^2 from Screening, Week 2 post transplantation and randomization to Months 6, and 12.
- To evaluate serum creatinine at various time points.
- To evaluate renal function and change in eGFR from screening, randomization, and Week 2 post transplantation to Months 6 and 12 eGFR in following subgroups: age ( $< 60$  and  $\geq 60$  years), gender, race, renal function strata ( $< 30$ ,  $30-45$ ,  $45-60$ ,  $\geq 60$  mL/min/1.73m^2, below/above 45 mL/min/1.73m^2, below/above 60 mL/min/1.73m^2), HCV status, lab MELD score categories ( $\leq 14$ ,  $15-19$ ,  $20-24$ ,  $25-29$ ,  $\geq 30$ ), and diagnosis leading to transplantation.
- To evaluate urinary protein/creatinine ratio at various time points.
- To evaluate the incidence of proteinuria of  $0.5-1.0$  g/day,  $1.0-3.0$  g/day and  $\geq 3.0$  g/day at various time points.
- To evaluate the incidence of and time to renal replacement therapy.

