#### **Everolimus**

Because everolimus is the mainstay of the protocol in the investigational arm (Arm 1), everolimus dose should be continued on a stable level according to trough levels. Treatment interruptions and dose reduction will be allowed for those patients who do not tolerate the prescribed dose of everolimus indicated by the occurrence of adverse events.

In both renal and heart transplantation, everolimus trough concentrations  $\leq$  3 ng/mL were associated with a significantly lower protection from acute rejection compared with trough levels  $>$  3 ng/mL. Although hyperlipidemia was common over the full exposure range, it responded to corticosteroid dose reduction, dietary management, and lipid-lowering therapies, and were, therefore, not dose-limiting. The incidence of leukocytopenia did not show any exposure-response relationship to everolimus trough concentrations. The incidence of notable thrombocytopenia ( $<$  100x10^9/L) increased with everolimus exposure; however, the incidence of clinically meaningful platelet reductions ( $<$  75x10^9/L) was generally low.

In severe hematologic adverse events (CTCAE 4.0) including leukocytopenia and thrombocytopenia everolimus should be interrupted until the condition has resolved. If a hemolytic uremic syndrome (hemolytic anemia, acute renal failure, uremia) occurs, everolimus has also to be permanently discontinued.

In case of a decrease of renal function all potential nephrotoxic medication other than the immunosuppressive agents should be discontinued first. If stadium 1 of acute kidney injury is met (an increase in SCr  $\geq 0.3$  mg/dL or  $25\mu\text{mol}/\text{L}$  (Chertow, 2005) or an increase in SCr of 50-100% from the initial value (Mehta, 2007)), everolimus and tacrolimus has to be reduced to the lowest trough levels according to the protocol (see above). If the acute kidney injury is not responsive to these measures, everolimus has to be discontinued.

Target therapeutic ranges for everolimus whole blood trough levels should be 3-8 ng/mL.

Dose should be adjusted if everolimus whole blood trough levels outside the target range are measured. Dose adjustments of everolimus should be monitored  $5 \pm 2$  days later by a measurement of the everolimus blood trough level.

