New onset diabetes mellitus	PT contains “Diabetes Mellitus” as Adverse event, but no PT containing “Diabetes Mellitus” as medical history
Hepatocellular Carcinoma (HCC)	HLT “HEPATIC NEOPLASMS MALIGNANT” OR “HEPATOBILIARY NEOPLASMS MALIGNANT UNSPECIFIED”
De novo HCC malignancies	HLT “HEPATIC NEOPLASMS MALIGNANT” OR “HEPATOBILIARY NEOPLASMS MALIGNANT UNSPECIFIED” as adverse event, but no HLT “HEPATIC NEOPLASMS MALIGNANT” OR “HEPATOBILIARY NEOPLASMS MALIGNANT UNSPECIFIED” as medical history

**Concomitant therapy of special interest** were defined as followed.

Concomitant therapy of special interest	Identification
Renal replacement therapy	PT „NON-DRUG THERPY: DIALYSIS“ or ATC CODE “B05Z (HEMODIALYTICS AND HEMOFILTRATES”

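### Under the SAP's definition of concomitant therapy, renal replacement therapy that starts after study treatment ends is not counted, dialysis already running at randomisation is, and time to RRT has no planned analysis

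*SAP*

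**What the plan says.** **Protocol.** Section 3.2 (renal function-related objectives) sets the aim: "To evaluate the incidence of and time to renal replacement therapy". Section 7.5 repeats it among the renal function variables. Neither place restricts it to time on study drug. Sections 6.6.3 and 6.6.8 require the Month 12 examination for all randomised patients, including those who stopped treatment early.

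**SAP, objective.** Section 1.3 rewords it: "To evaluate the incidence of and time to renal replacement therapy as concomitant therapy of special interest".

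**SAP, identification.** Section 5.5.2 has a row "Renal replacement therapy", identified by a dialysis preferred term or the ATC group "B05Z (HEMODIALYTICS AND HEMOFILTRATES". The row gives codes only. It has no onset condition, follow-up window or censoring rule.

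**SAP, meaning of concomitant.** Section 2.3.2, which also covers non-drug therapies and uses the Safety Set, says: "Concomitant medication are medication, which were treated on at least one in the time interval randomization and last day of study treatment". The preceding sentence reads: "Prior medication are defined as medication, which started 1 or more days before randomization". The section title mentions post therapies, but the SAP does not define them.

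**SAP, last day of treatment.** Section 2.1.1 takes the later of the last end date on the Dosage Administration Record and, from the End of Treatment form, the "Last known date subject took study treatment".

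**SAP, other events.** Section 5.5.2 counts rejection, graft loss and death from Visit 2 to Day 360 with no on-drug condition. RRT is not among those events, nor in the endpoint lists of section 2.5.1.

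**The concern.** An objective covering 12 months of follow-up in all randomised patients appears to have become an on-treatment tabulation. Three things follow if the SAP is applied as written.

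- RRT that begins after the last treatment day falls outside the definition.
- RRT that began before randomisation and was still running falls inside it, because one overlapping day is enough and onset plays no part.
- The time-to-event half of the objective has no origin, event definition, censoring rule or output.

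The first matters most because kidney problems can themselves end treatment. On acute kidney injury, Protocol 6.6.3 states: "If the acute kidney injury is not responsive to these measures, everolimus has to be discontinued". Sections 6.6.3 and 6.6.6 also stop everolimus for haemolytic uraemic syndrome and for suspected thrombotic microangiopathy. Under section 6.6.2, a patient who leaves the assigned regimen is discontinued from study drug. The counting window could therefore close shortly before dialysis begins. The tacrolimus part of section 6.6.3 has no matching kidney-injury rule, so the loss could differ between arms.

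SAP section 4 declares the change in how proteinuria is handled. It says nothing about RRT, so a reader of the results would not know that the objective had been narrowed.

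**Working it through.** The plan states no RRT rate, event count or power for this objective, so there is no figure to reproduce. The check applies the written rule to example episodes and compares it with incident RRT over follow-up.

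**Inputs.** Day 1 is Visit 2, since SAP 5.5.2 computes day as date minus baseline date plus 1. Let S and E be the start and end day of a dialysis episode, and L the last day of study treatment.

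- SAP 2.3.2 rule: counted if S ≤ L and E ≥ 1.
- Incident RRT on the SAP 5.5.2 event window: counted if 1 ≤ S ≤ 360.

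**Examples (episode days are assumed, for illustration only).**

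| Case | S to E | L | SAP 2.3.2 rule | Incident, Day 1–360 |
|---|---|---|---|---|
| a. Dialysis running at randomisation | −5 to 10 | 360 | counted (also prior) | no |
| b. Treatment ends Day 90, then dialysis | 95 to 120 | 90 | not counted (95 > 90) | yes |
| c. Dialysis before treatment ends | 85 to 120 | 90 | counted (85 ≤ 90) | yes |
| d. As b, but L moved to Day 360 | 95 to 120 | 360 | counted | yes |
| e. Dialysis on treatment | 100 to 130 | 360 | counted | yes |

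The two rules disagree in cases a and b. Cases b and d are the same patient and differ only in how the last treatment day is read.

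**Follow-up left uncovered.** For a patient followed to Day 360 whose treatment ends on Day L, the uncovered time is 360 − L days:

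- L = 30: 330 days (330/360 = 92%)
- L = 90: 270 days (75%)
- L = 180: 180 days (50%)
- L = 270: 90 days (25%)

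This is the gap per patient, not a number of lost events. That number would need the RRT rate after drug stop and the discontinuation rate by arm, and the documents give neither. SAP 2.3.6 reports fewer than 20% study discontinuations, but that concerns leaving the study, not stopping the drug.

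**Windows the SAP uses elsewhere.** Efficacy events run to Day 360 (5.5.2). Treatment-emergent adverse events are those from baseline onward, with no end at drug stop (2.6.1). Laboratory values count as on-treatment up to 28 days after discontinuation (2.6.3). Under 2.3.2, RRT has no post-treatment window at all.

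**Dialysis at randomisation.** Protocol 5.1 excludes RRT lasting more than 2 weeks before transplantation and requires eGFR above 30 mL/min/1.73m² at randomisation. No criterion names ongoing dialysis. Dialysis itself lowers creatinine, so case a is possible but should be uncommon.

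**The case against.** **The definition is worded for medication.** Applying it to dialysis is an inference. That stands as a caveat. But section 2.3.2 also deals with non-drug therapies, the SAP itself labels RRT a concomitant therapy, and no other window is offered.

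**Stopping everolimus need not end study treatment.** SAP 5.1.1 treats tacrolimus as study medication and moves everolimus and tacrolimus records made after discontinuation into study medication, up to the last visit. A patient who stays on tacrolimus could then still be inside the window, as in case d. This is the strongest counter-argument, and it makes the text ambiguous. It does not settle the matter: the stated purpose is treatment duration and mean dose, and section 2.1.1 ties the last treatment date to two named forms. A patient on neither drug would be cut off on either reading.

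**Ongoing dialysis can be separated.** A therapy begun before randomisation also meets the definition of prior, and time to RRT implies an onset date. This is fair, but the SAP does not say that such episodes are left out of the incidence.

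**A stronger reading a reader might infer.** From the everolimus stopping rule, one could conclude that the loss of events flatters the everolimus arm. The documents do not support that. Section 6.6.2 discontinues patients in either arm who leave their regimen, the withdrawal rules in section 5.2 apply to both arms, and section 10.4.2 foresees control patients switching. No discontinuation rates by arm or reason are given, so any numerical example of the distortion would rest on invented inputs.

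**Impact is limited.** RRT is one of many secondary objectives, with no confirmatory test and no power calculation. Renal adverse events after drug stop still reach the adverse event tables.

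**Conclusion.** The point holds as a defect of definition. On its literal wording the SAP omits RRT that begins after study treatment ends and includes RRT already under way at randomisation, and it plans no analysis of time to RRT. This goes beyond missing detail, because the only rule stated gives a count that differs from the protocol's objective.

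The conclusion rests on two assumptions: that section 2.3.2 governs dialysis, and that section 5.1.1 does not move the last treatment day. The first is the natural reading. The second is likely but not certain.

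The size is modest. Up to 360 − L days of follow-up per discontinued patient are uncovered, in an exploratory secondary objective. The loss could differ by arm, because the explicit rule for unresponsive kidney injury names everolimus only. Neither the direction nor the size of any bias can be established from the documents. The inclusion of ongoing dialysis is the smaller issue.

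**What to change.** In SAP 1.3 and 5.5.2:

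- Derive RRT in the Full Analysis Set as the first episode with onset from Visit 2 to Day 360, whether or not the patient is still on study drug.
- Use the time origin and censoring that section 5.5.2 already sets for rejection, graft loss and death.
- Report RRT ongoing at Visit 2 separately, not as an incident event.
- Add RRT to the Kaplan-Meier outputs.
- List the change in section 4.

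**Cost.** One derived event, some SAP wording and one extra output. Using the Full Analysis Set rather than the Safety Set is partly a matter of choice. It keeps RRT in line with the other event endpoints.

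**Limitation to state.** Protocol 6.6.5 requires significant non-drug therapies to be recorded. However, the list in section 7 of what is collected after premature drug discontinuation does not name dialysis. Completeness after drug stop must be checked and reported as a limitation, since a change of wording cannot recover records that were not made.
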